### 5.3.3 Follow-up (post-index) period

The duration of follow-up is for a maximum of 37 days from index date.

IV LCM treatment may span several days; treatment will be considered continuous if subsequent IV LCM treatment is noted to occur within 7 days of a previous treatment. If 7 days pass without a documented iv or LCM treatment, the index exposure has ended. Follow then continues until end of follow up or until the following censoring conditions apply:

Censoring: Patients will be followed for either 37 days OR until the patient is lost to follow-up[transfer out]; OR the patient is discharged from the in-patient setting [events that occur at home are not easy to track and are not included here; outpatient setting events are also excluded as we do not know what the patient has been doing at home during routine care]; OR the patient dies; OR the patient switches to another AED instead of/or adjunct to LCM; whichever comes first.

Clarification of follow up: The purpose of the study is to evaluate iv loading dose and higher subsequent dosing risk. Some patients may receive only one iv loading dose and then transfer to oral dosing which may last some weeks in the hospital setting. In the case where a patient has just one dose of iv LCM and switches to continuous oral LCM therapy, the follow up for AE evaluation will cease after a maximum of seven days of oral therapy or until censoring occurs as above. The same applies for those exposed to one dose of iv LCM and no further LCM exposure (either oral or iv).

Patients who have more than one dose of iv LCM and then switch to oral therapy will have a maximum follow up of 37 days of follow up index date or until censoring.

Patient time is contributed until either end of follow up or censor point (in days).

Patients are only included once in this study, so if we find evidence of a further iv loading dose of LCM given 6 months later say, they do not contribute to the study.

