## **5.5 Variables**

### **5.5.1 Primary outcome measure**

The following primary variables will be measured to meet the study objectives:

- The incidence rate and incidence rate ratio of cardiac disorders (selected preferred terms (PTs) as described in Section 5.5.5)
- The incidence rate and incidence rate ratio of general disorders and administration site conditions (selected PTs as described in Section 5.5.5)
- The incidence rate and incidence rate ratio of injury, poisoning and procedural complications (selected PTs as described in Section 5.5.5)
- The incidence rate and incidence rate ratio of investigations (i.e. the incidence rate of ECG PR prolongation)
- The incidence rate and incidence rate ratio of skin and subcutaneous tissue disorders (selected PTs as described in Section 5.5.5)
- The incidence rate and incidence rate ratio of drug reactions with eosinophilia and systemic symptoms syndrome (selected PTs as described in Section 5.5.5)
- The incidence rate and incidence rate ratio of severe cutaneous adverse reactions (selected PTs as described in Section 5.5.5)
- The incidence rate and incidence rate ratio of hypersensitivity (selected PTs as described in Section 5.5.5)
- The incidence rate and incidence rate ratio of nervous system disorders (selected PTs as described in Section 5.5.5)
- The incidence rate and incidence rate ratio of metabolism and nutrition disorders (selected PTs as described in Section 5.5.5)

- The incidence rate and incidence rate ratio of psychiatric disorders (i.e. abnormal behavior)

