## 5.6 Data source and data management

### 5.6.1 Description of database

PEDSnet (pedsnet.org) is a clinical research network (CRN) that was launched in 2014 and is currently a Clinical Data Research Network (CDRN) in member of the Patient-Centered Clinical Research Network (PCORnet, pcor.net). PEDSnet includes 8 pediatric health systems across the United States including Boston Children’s hospital, Children’s Hospital Colorado, Children’s Hospital of Philadelphia, Cincinnati Children’s Hospital Medical Center, Nationwide Children’s Hospital, Nemours Children’s Health System, St Louis Children’s Hospital and Seattle Children’s Hospital. The PEDSnet core data includes information on 6.2 million children, seen since 2009. The regional catchment area for the network extends across 22 states in the US, currently providing care annually for 2.5 million patients, or 2.8% of all children in the USA, from diverse demographic, geographic, and socioeconomic backgrounds. The historical database from 2009-present includes 6.5 million children inclusive of all their inpatient and outpatient care that occurs in member institutions.

The PEDSnet database consists of data from electronic healthcare records (EHRs) generated during a health encounter at any of the health institutions included in the network. The data includes demographic characteristics, encounter data for primary care, specialty care, emergency department and inpatient visits, procedures, prescribed or dispensed medications, laboratory results, diagnoses, anthropometrics and vital signs collected during routine care or management of complex illnesses, [Table 4 Measures available in the PEDSnet database](#).

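### Severe skin reactions that start after discharge, after an added AED or after the single-dose cap go uncounted even when PEDSnet records them, so a low rate says nothing about delayed reactions

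*Protocol*

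**What the plan says.** Section 5.3.3 sets the outer limit: "The duration of follow-up is for a maximum of 37 days from index date". It then lists events that end follow-up earlier. One is discharge: "OR the patient is discharged from the in-patient setting". The bracket attached to it gives two reasons, that "events that occur at home are not easy to track and are not included here" and that "outpatient setting events are also excluded as we do not know what the patient has been doing at home during routine care". Another is a change of treatment: "the patient switches to another AED instead of/or adjunct to LCM". For a child who has one IV dose and then moves to oral lacosamide, "the follow up for AE evaluation will cease after a maximum of seven days of oral therapy", and the same limit applies if no more lacosamide is given. Children with more than one IV dose who switch to oral can be followed to day 37 unless censored.

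Section 5.5.1 lists among the primary measures "The incidence rate and incidence rate ratio of drug reactions with eosinophilia and systemic symptoms syndrome", and likewise severe cutaneous adverse reactions. Section 5.5.2 lists SJS and TEN as secondary.

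Section 5.6.1 describes the database as "inclusive of all their inpatient and outpatient care that occurs in member institutions", and Table 4 lists emergency, inpatient and outpatient encounters. Section 5.9.4 concedes that outpatient and emergency records are less complete, but still expects severe events to be recorded.

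Of the four sensitivity analyses in Section 5.9.1.4, one concerns the length of follow-up, and it shortens it.

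**The concern.** The rule discards events that the data source holds. Take a child discharged on day 4 and readmitted to the same hospital on day 15 with DRESS. The readmission is in the common data model, but the event is not counted. The difficulty of tracking events at home does not explain leaving out an in-network readmission or emergency visit.

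At stake is how a low or zero rate for these outcomes will be read. Sections 1, 5.1 and 5.9.1.2 still describe follow-up to 30 days after stopping treatment. A reader of those sections would take a zero as covering about a month after exposure, when it may cover only a few inpatient days.

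**Working it through.** The protocol has no power, precision or event calculation to reproduce. Section 5.9.3 gives only a feasibility count of 875 children with at least one IV administration, before the full criteria.

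**1. The rules side by side**

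- Section 5.3.3: earliest of 37 days, transfer out, discharge, death or another AED, with the shorter cap after a single IV dose.
- Section 1: up to 30 days after stopping lacosamide, or censoring.
- Section 5.1: up to 30 days after stopping IV lacosamide. Discharge and an added AED are not mentioned.
- Section 5.9.1.2: for children without the event, IV discontinuation plus 30 days or loss to follow-up, yet the same section refers to 5.3.3 for person-time.

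These do not define the same window.

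**2. Share of events observable**

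Inputs from the protocol: the 37-day limit, and the single-dose cap taken as day 7 from index. That is approximate, because the cap is worded as seven days of oral therapy. 7/37 = 19% of the window.

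Assumed inputs: onset uniform between days a and b, and time to discharge or added AED exponential with mean m = 3, 7 or 14 days. With cap c and e = min(b, c), and a < e,

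share = m/(b − a) × [exp(−a/m) − exp(−e/m)], and 0 if the cap comes at or before a.

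Examples:
- Days 0–7, m = 3: 3/7 × (1 − 0.097) = 39%.
- Days 7–37, cap 37, m = 14: 14/30 × (0.607 − 0.071) = 25%.

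| Assumed onset | Single dose, cap 7 (m = 3, 7, 14) | Multiple doses, cap 37 (m = 3, 7, 14) |
|---|---|---|
| First 24 hours | 85%, 93%, 97% | 85%, 93%, 97% |
| Days 0–7 | 39%, 63%, 79% | 39%, 63%, 79% |
| Days 0–37 | 7%, 12%, 15% | 8%, 19%, 35% |
| Days 7–37 | 0%, 0%, 0% | 1.0%, 8.5%, 25% |
| Days 14–37 | 0%, 0%, 0% | 0.1%, 4.0%, 18% |

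**3. Effect on the rate per patient-day**

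Censoring removes time as well as events, so the share lost is not itself the bias in a rate. For rare events under the 37-day cap, mean follow-up is m × [1 − exp(−37/m)] = 3.0, 7.0 and 13.0 days, or 8.1%, 18.8% and 35.1% of 37 days. Dividing the share of events kept by the share of time kept gives:

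- Onset uniform over days 0–37: ratio 1, so no distortion.
- Onset on days 7–37: 0.0097/0.081 = 0.12, 0.085/0.188 = 0.45 and 0.25/0.351 = 0.71 of the rate that full 37-day follow-up would give. Under the single-dose cap the ratio is 0.

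**4. How much is rarity**

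At an assumed 37-day risk of 1 in 1,000 in all 875 children, full follow-up expects 875 × 0.001 = 0.88 events, and the chance of at least one is 1 − 0.999^875 = 58%. If only 7/37 of events are observable, the expectation is 0.88 × 7/37 = 0.17 and the chance 15%. At 1 in 10,000 the expected counts are 0.09 and 0.02. Zero events in 875 fully followed children gives a 95% upper bound on risk of 1 − 0.05^(1/875) = 0.34%.

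**The case against.** The strongest objection is that the protocol does not give the inputs that decide the size: onset latency, length of stay, time to an added AED and the share with a single dose. Its only current statement on timing, in Section 5.9.4, expects most events within 24 hours, and onset that early leaves 85% to 97% observable. This stands. A reader might infer that these outcomes can hardly be observed at all, and the documents do not support that. The 24-hour statement is not specific to skin reactions, so it does not settle the matter the other way either.

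Second, the measure is a rate per patient-day, and Section 5.9.1.2 already warns that events concentrated early or late break the constant-rate assumption. This also stands: a short window distorts the rate only when the hazard is not constant. The warning does not tell the reader that follow-up is inpatient-only or that recorded events are set aside.

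Third, counts would be low anyway in at most 875 children. A reader might infer that a near-zero rate would be the product of the censoring rule. Step 4 shows that rarity could produce it alone.

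Fourth, the censoring has reasons. What happens at home after discharge is unknown, and Section 15, item 1e, explains that a later AED confounds attribution. Both are fair grounds for the main analysis. Multi-dose inpatients without another AED can also still reach day 37.

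**Conclusion.** The point holds in a limited form. By rule, and without any assumption, a DRESS, severe cutaneous or SJS/TEN event that starts after discharge, after an added or replacement AED, or after the single-dose cap is not counted, even when it is recorded inside PEDSnet. None of the listed sensitivity analyses lifts this censoring.

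The size is conditional on assumed onset and on mean times to censoring of 3 to 14 days. The loss is moderate if onset is in the first week (39% to 79% observable). It is near-total to large if onset is on days 7 to 37 (0% observable for single-dose children, 1% to 25% for multi-dose). A low or zero rate therefore cannot be taken as evidence of safety for delayed reactions. Nor can it be attributed to the censoring alone.

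The differing follow-up rules in Sections 1, 5.1, 5.3.3 and 5.9.1.2 are a documentary defect that needs no assumption.

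**What to change.** Keep the main rule and make three changes.

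1. Add to Section 5.9.1.4 a sensitivity analysis for DRESS, severe cutaneous reactions and SJS/TEN. It follows every child to day 37 through any PEDSnet encounter (readmission, emergency or outpatient), without censoring at discharge or at the single-dose cap. Show it both with and without censoring at an added AED, so that the attribution concern in Section 15 stays visible.
2. Label the main results for these outcomes as in-hospital rates only.
3. Reconcile the follow-up and censoring rule in Section 5.3.3 with the 30-days-after-discontinuation text in Sections 1, 5.1 and 5.9.1.2, so that one window defines person-time.

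The cost is one extra analysis on data already in the common data model, plus text edits. The downside is that out-of-network events are still missed and that later AEDs may contribute to some of the added events. With outcomes this rare the analysis may still return no events, but its window would then be stated and longer.

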### **5.9.1.2 Analysis of primary and secondary outcome measures**

Only the first occurrence of the event after the index date will be counted in analyses. For both the IV LCM group and comparator group, counts and frequency of events will be recorded. For both the IV LCM high dose group and comparator group, several incidence rates will be calculated. First, the overall incidence rate of any event of interest will be calculated. Second, incidence rates for each of the following events will be calculated individually: Cardiac disorders, Skin and subcutaneous tissue disorders, Nervous system disorders, Metabolism and nutrition disorders, Psychiatric disorders, Injury, poisoning and procedural complications, General disorders and administration site conditions, and Investigations, Drug reaction with eosinophilia and systemic symptoms syndrome, Severe cutaneous adverse reactions and Hypersensitivity events. Third, incidence rates for each subcategory of the abovementioned events and associated 95% confidence intervals will be calculated. The incidence rate of each event with associated 95% confidence interval will be calculated for the IV LCM high dose group and comparator group.

The numerator will be the total number of patients with the outcomes identified during the follow-up period. The denominator will be in patient-days. That is, the total summation of individual patient-days at risk up to the first occurrence of the AE of interest for subjects with

that AE, and the total patient-days at risk calculated up to the censoring date i.e. discontinuation of IV LCM plus 30 days or loss to follow-up for those subjects not experiencing that AE. Incidence rates will be presented with a 95% exact confidence interval based upon the Poisson distribution or another relevant model if there is nonconvergence. It is important to note incidence rates per time at risk are based on a constancy assumption. That is, the rates per unit of time assume that the event occurs with a constant rate over time. Events that are more likely to occur early or late relative to the initial exposure or with an increasing or decreasing hazard rate over time would not meet the constancy assumption and these rates should be viewed with caution. The person time for each patient will be calculated as the total number of days of follow-up as described in Section 5.3.3 .

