### 5.9.4 Strength and Limitations

**Unmeasured confounding:** As the study is comparing the incidence rates of select medical events in patients who are treated with a high dose of IV lacosamide to patients who are treated with recommended dose of IV lacosamide, the major confounders are factors that impact the incidence rate of these medical events of interest. These factors include age, gender, comorbidities, and exposure to other medications which are measured. Unmeasured confounding would only occur if there was a major confounder which is not measured and thus missed from the adjusted model. However, the electronic medical records include demographic information, the medical history of the patients and any medications prescribed by the physicians. Therefore we anticipate that information on most of the confounders will be available. It is possible that there will be missing information on some comorbidities, if they are not recorded by the physicians and on medications that are either bought over counter or prescribed outside the PEDSnet healthcare network. Nevertheless, most hospitals in the PEDSNet healthcare network are large with epilepsy comprehensive care centers within the neurology departments, so we anticipate reliable background medical. We do not anticipate that there will be a disproportionate difference in the recording of the medical history data and prescription of medications in patients who are treated with high dose lacosamide and recommended lacosamide prior to the index date. Therefore, we anticipate that there will be minimal unmeasured confounding. Additionally, the analysis will be using new user design to minimize confounding by indication.

**Reduced generalizability:** The PEDSnet database is restricted to subjects seeking and receiving medical care within a facility affiliated with PEDSnet. Data is obtained from multiple care sites and type (e.g. in-patient, out-patient, emergency department). However, if a report of an event was made or a subject was treated for an event at a facility that is not affiliated PEDSnet, this information will not be captured in the PEDSnet data. However, as most events are anticipated to occur within 24 hours of receiving IV LCM, the impact of this is likely to be low.

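### Follow-up length depends on what happens after the index dose, so with early-clustered events the per-patient-day IRR can differ from 1 without any dose effect, in either direction

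*Protocol*

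**What the plan says.** Group membership is fixed by the first dose and does not change (Section 5.2). Follow-up is then governed by Section 5.3.3:

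- Overall limit: "The duration of follow-up is for a maximum of 37 days from index date".
- One IV dose, then oral LCM: "the follow up for AE evaluation will cease after a maximum of seven days of oral therapy or until censoring occurs as above". The same limit applies if no LCM follows at all.
- More than one IV dose: "Patients who have more than one dose of iv LCM and then switch to oral therapy will have a maximum follow up of 37 days".
- Earlier end at discharge, death or transfer, or if "the patient switches to another AED instead of/or adjunct to LCM".

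The primary measures are incidence rates and IRRs (Section 5.5.1), with patient-days as denominator and only the first event counted (5.9.1.2). The IRR comes from Poisson regression with inverse probability weights (5.9.1.1, 5.9.1.5), and the propensity model uses baseline characteristics only. Section 5.9.1.2 notes that "the rates per unit of time assume that the event occurs with a constant rate over time" and advises caution for events that come early or late. Section 5.9.4 states that "most events are anticipated to occur within 24 hours of receiving IV LCM".

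Other sections describe follow-up differently. The Executive Summary, Section 5.1 and the denominator paragraph of 5.9.1.2 run it to 30 days after LCM is discontinued, without the 7-day and 37-day limits.

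**The concern.** The number of IV doses and the addition of another AED are both settled after the group is assigned. Weights built on baseline covariates balance them only as far as those covariates predict them.

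If events cluster on day 1, later patient-days add to the denominator and little to the numerator. A group with longer follow-up then shows a lower rate at the same risk per child. The plan itself expects this clustering, so it expects its constant-rate assumption to fail, yet it attaches a caution and no alternative estimate.

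There are reasons to expect the follow-up mix to differ by dose group. Section 5.1 assumes that loaded children are more often in status epilepticus and refractory. Section 5.3.3 expects some loaded children to receive one IV dose and then go to oral treatment. Section 5.5.4 defines a loading dose as followed within about 12 hours by a lower maintenance dose, route not stated. These do not all point the same way.

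At stake is the primary safety comparison. A ratio pushed above 1 suggests harm from follow-up length alone; one pushed below 1 could hide harm. Also, events after the 7-day limit cannot be seen in single-dose children but can be seen in the others.

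**Working it through.** The protocol gives no event rate, single-dose share or length of stay, so there is no stated figure to reproduce. Every input below except the 7-day and 37-day limits is an assumption. The 7 days are taken from index; after an oral switch they count oral therapy, so the true limit is slightly later. The shares stand for the mix left after weighting.

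**Check 1: number of IV doses, no dose effect.** Day-1 risk is 10% in both groups, so h1 = -ln(0.9) = 0.1054. The later hazard is h2 per day. For limit T without discharge:

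- events per child: E(T) = 1 - 0.9·exp(-h2·(T-1))
- days per child: Y(T) = 0.1/h1 + 0.9·(1 - exp(-h2·(T-1)))/h2

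With h2 = 0.0001: E(7) = 0.1005, Y(7) = 6.35; E(37) = 0.1032, Y(37) = 33.29.

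- 60% single-dose: (0.6·0.1005 + 0.4·0.1032)/(0.6·6.35 + 0.4·33.29) = 0.1016/17.12 = 0.00593 per day
- 30% single-dose: 0.1024/25.21 = 0.00406 per day
- ratio 1.46; with the shares exchanged, 1/1.46 = 0.685

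For discharge, hazard and survival are integrated against exp(-t/m), where m is the mean stay in days. Each cell gives the null IRR for 60% (high) vs 30% (recommended) single-dose children, then for the shares exchanged:

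| Mean stay | h2 = 0.01%/day | h2 = 0.5%/day |
|---|---|---|
| no discharge | 1.460 / 0.685 | 1.205 / 0.830 |
| 20 days | 1.313 / 0.761 | 1.187 / 0.842 |
| 10 days | 1.201 / 0.833 | 1.138 / 0.878 |
| 5 days | 1.085 / 0.922 | 1.066 / 0.938 |
| 3 days | 1.030 / 0.971 | 1.025 / 0.975 |

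**Check 2: a different hazard model, no discharge.** The 37-day risk is 5% or 15%, with a chosen share of the total hazard on day 1. IRR = rate(high)/rate(recommended), where rate = Σw·(1 - S(T)) / Σw·∫S over the mix of limits T, w being the share of children with limit T and S the event-free probability. The IRRs are nearly the same for both risks.

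| Scenario (high vs recommended) | 30% on day 1 | 50% | 80% |
|---|---|---|---|
| one-dose share 30% vs 70% | 0.80 | 0.70 | 0.61 |
| one-dose share 40% vs 60% | 0.90 | 0.84 | 0.79 |
| one-dose share 70% vs 30% | 1.26 | 1.42 | 1.63 |
| AED added on day 3 in 50% vs 20% | 1.20 | 1.30 | 1.40 |

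In the AED scenario the remaining children split equally between the 7-day and 37-day limits. With a constant hazard, or with the same mix in both groups, the IRR is 1.000.

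**Check 3: false positives.** Each scenario used 2,000 simulated studies, 300 children per group, robust variance and a two-sided 5% test, with 50% to 80% of hazard on day 1. The 30% vs 70% scenario rejects in 13-22% (5% risk) and 29-54% (15% risk) of studies. The AED scenario rejects in 9-14% and 16-26%. Weighting was not simulated.

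**Check 4: common windows from index.** A 7-day window returns the dose-count scenarios to 1.000, with 3-5% rejection in the 30% vs 70% scenario. The AED scenario still gives 1.17-1.23 at 7 days. It gives 1.000 at 24 hours, since nobody in that scenario is censored before then.

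**The case against.** The case against is substantial.

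- **Two conditions are needed.** The hazard must vary over time and the follow-up mix must still differ after weighting. The first is the plan's own expectation. The second is plausible but has no figure behind it, and weighting on diagnoses and prior treatment may remove part of it. This stands.
- **Discharge ends follow-up for everyone.** It compresses the 7-versus-37-day contrast, as the short-stay rows show. This stands; the no-discharge figures are an outer bound for the chosen shares and hazards.
- **A child who reacts is not credited with a shorter limit.** Only the first event counts and patient-days stop there, so for that AE the limits act on children who do not have it. This stands.
- **The plan already responds in part.** It prints a caution, reports counts and frequencies beside the rates, and has a sensitivity analysis without the 30 days after discontinuation (5.9.1.4). Section 15 (item 1e) gives attribution of the signal as the reason for censoring at an added AED. None of this equalises follow-up, because treatment duration still varies, but the censoring has a stated purpose.
- **Under the competing rule the contrast would not apply.** If follow-up ran to 30 days after discontinuation, the 7-versus-37-day difference would not arise. This makes reconciling the sections the first step.

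A reader might also take the 24-hour and 7-day periods in the Executive Summary as windows from the index dose. There they run after IV LCM is discontinued and apply only to the loading-dose stratification.

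**Conclusion.** The point holds in conditional form. With events expected mostly within 24 hours, the primary IRR can differ from 1 with no dose effect whenever the follow-up mix still differs between groups after weighting.

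A reader might infer that the IRR must be biased, or that it must be inflated. The documents support neither: if either condition fails the null IRR is 1, and no single-dose share is given. More single-dose children or earlier added AEDs in the high-dose group push the ratio up; more multi-dose children there push it down. These can offset each other, and their net effect was not modelled. Nor was informative censoring, where adding an AED tracks severity or AEs.

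The size rests wholly on assumed shares, risks and stays. For 60% and 30% single-dose shares it runs from material without discharge or with a 10-day mean stay to negligible with a 3-day mean stay. The rule and the measure are both fixed in the protocol, so this is not a detail awaiting the SAP.

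**What to change.** 1. Reconcile the follow-up rule in the Executive Summary, Section 5.1 and Section 5.9.1.2 (discontinuation plus 30 days) with Section 5.3.3, so that the denominator has one definition.
2. Estimate the main IRR and a risk ratio in common windows from the index dose for all children, 0-24 hours and 0-7 days, or split the rates at those times. Keep the variable-length rate as secondary.
3. For delayed skin and hypersensitivity events, use one maximum window for all children, whatever the number of IV doses.
4. Keep censoring at an added AED as the stated rule, for the attribution reason given in Section 15. Add a sensitivity analysis that does not censor there or that weights for that censoring, because the 7-day window alone does not remove this artefact.

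The cost is protocol and SAP wording and a few extra runs of the same model on data already extracted. The main estimate would rest on fewer patient-days.
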